5.1.1. Potential Confounders and Strategy to Limit Impact

Severity of initial illness: Randomization should achieve balance at baseline. Adjustment for SNAPPE scores on admission to the NICU will be performed during the analysis of the primary outcome.

Site Variation: Randomization will be stratified by site.

General respiratory management in the DR and beyond: Local unit protocols will be followed with respect to aspects of respiratory support not specifically addressed in the study interventions. In general, after initial resuscitation, CPAP will be the initial mode of respiratory support in reasonably vigorous infants. Intubation will be reserved for infants who remain apneic, are without adequate respiratory effort, or have persistent bradycardia. Surfactant for RDS prophylaxis will not be given in the DR prior to SI (if so randomized), even if the infant is intubated. Caffeine will be administered to infants if needed for respiratory support.

Extubation and intubation guidelines: Continued need for mechanical ventilation is associated with BPD. We adopt a uniform guideline to intubation and extubation, though clinical circumstances may preclude strict adherence to guidelines at all times. There is no consensus about weaning babies from mechanical ventilation. Therefore, the proposed extubation guidelines are based on consensus and criteria used in several current and recent large clinical trials. On a daily basis the infant will be assessed for ability to wean from ventilation. We will strongly encourage extubation to be attempted within 24 hours after meeting all following criteria: $PCO_2 \leq 55$ mm Hg and a $pH \geq 7.25$, FiO_2 of ≤ 0.4 with an SpO_2 of $\geq 88\%$ or higher, mean airway pressure of ≤ 8 cm of water, and hemodynamic stability and without evidence of clinically significant patent ductus arteriosus. All infants will have received caffeine prior to an extubation attempt. Extubation may be attempted at higher settings at the discretion of the clinical team. Following extubation all infants should be placed on nasal CPAP or NIPPV, not on nasal cannula or oxihood. In unplanned extubations, the infant will be given an opportunity to remain extubated, if heart rate and oxygen saturations are maintained without excessively high FiO_2 or work of breathing. Extubation will be considered successful if the infant remains extubated for at least 48 hours. Reintubation will be at the discretion of the clinical team managing the infant.

Demographic variables: The next section describes the analytical plan to examine the key covariates of gender, antenatal corticosteroids, multiples, and week of gestation.¹⁹

All of these instructions and definitions will be written into an Operating Manual to be used as the initial source for teaching sites and their staff, and on-going re-education.

6. Statistical Analysis

The Data Coordinating Center (DCC) will be housed at the University of Pennsylvania and submitting a separate IRB approval request to the IRB. The DCC is comprised of four parts: Biostatistics, Project Management, Data Management and Research Technology.

Biostatistical support will provide centralized randomization, publication support, interim analyses and statistical analysis plans under the direction of Drs. [name] and [name]. Project management will coordinate activities between the scientific and operations teams and manage sites. Data Management will include case report form (CRF) design, management and entry, data quality assurance and reporting. Information Systems will include database design and system support.

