The underlying trial rationale is that augmenting PEEP by a SI will facilitate clearance of lung fluid and more effectively develop a stable FRC. The SAIL trial will promote evidence-based practice, by conducting a 600 patient prospective multi-center trial targeting clinically important outcomes. SAIL will randomize eligible infants to one of two methods of ensuring early DR lung aeration: the initial delivery of PEEP alone; or PEEP supplemented by SI. The combined primary outcome, BPD or death at 36 weeks, is well established, robust and clinically meaningful. Treatment assignment will be masked at the time of developmental follow-up and the outcome of BPD will be according to a blinded assessment of the Oxygen Reduction Test (ORT).¹ The SAIL trial addresses two unanswered, but important questions:

Firstly, “In preterms 23-26 weeks (GA) who require resuscitation and/or respiratory support in the DR, which of two alternative strategies to achieve lung aeration results in the lowest rate of death or BPD at 36 corrected weeks of age?”

Secondly, “In preterms 23-26 weeks (GA) who require resuscitation and/or respiratory support in the DR, what are the safety profiles of 2 currently used methods in the DR to achieve lung aeration?”

In addition to this primary outcome, we will describe several clinically relevant and/or physiologically relevant secondary outcomes, including: FiO₂, respiratory support, surfactant use, radiographic evidence of RDS, % of infants ever intubated, head ultrasound, duration of respiratory support; respiratory severity score (FIO₂ x mean airway pressure).

There are two defined ancillary studies that will be conducted within the trial. At one site (Ulm) we will have nirosopy brain recordings, and at several sites, we will obtain flow volume pressure records during and after SI in the DR.

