Eligibility and Randomization Data Form	Clinical data: meets inclusion criteria and none of exclusion criteria; eligibility confirmed Research: date and time of randomization, and allocation of treatment arm (control vs intervention)	First 30 seconds of birth
Delivery Room (DR) Data Form	RESEARCH DATA collected: time infant is placed on resuscitation trolley; time of specific maneuver; 1 st sustained inflation and exact pressure measurement x 15 seconds; time of 2 nd sustained inflation and exact pressure measurement x 15 seconds; and use of ventilator vs T-piece	Research intervention takes place within the first 30 seconds up to 1 - 2 minutes of life
	Clinical data: time of birth, time of cord clamping, NRP guidelines used in the resuscitation of the infant such as respiratory status; blood gas values including glucose and hemoglobin/hematocrit values; procedures if any (intubation, chest compression, administration of epinephrine; surfactant delivery; UAC/UVC placement; chest tube placement and additional medications; final respiratory status before leaving DR; and outcome of resuscitation. Additional clinical information: date and time of birth, birth weight, Apgar score at 1 and 5 min, and gender	Certain clinical time points as dictated by the resuscitation process in the DR; data should be completed within first 48 hours

Data Collection Topic	Specific Data Elements	Specific time interval
Respiratory function measurements of inflations and physiologic monitoring (Obtained only at a subset of sites)	Inflation characteristics: pressure, flow, tidal volume, exhaled CO ₂ Physiologic monitoring: heart rate, oxygen saturation, delivered oxygen concentration	First 10 minutes of life
Delivery Room Video recording (obtained only at a subset of sites; transferred and destroyed after analysis)	Video recordings of the infant during the initial resuscitation and stabilization	Up to the first 30 minutes of life
Adverse Events	See Section 9.2 for detailed information.	Specific events during the first 10 days of life; thereafter continuing AE reporting structures are in place until the infant reaches 36 weeks GA
SNAPPE Score	Clinical data: severity score that is compiled by using clinical parameters within the first 12 hours of life, such as lowest pH, PaO ₂ and corresponding FiO ₂ and MAP, urine output and presence of seizures	Completed by first week of life

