6.1.2.2. Analysis of Primary Outcome

The primary endpoint to be used for efficacy evaluation is the rate of Death or BPD at 36 weeks gestation age. The primary hypothesis to be tested is that the treatment therapy results in a decreased event rate. Although a proportion's test is used for sample size calculations, rates will be compared using logistic regression, which will allow for control of covariates, as well as investigation of effect modification. Potential covariates include gender, gestational age, initial heart rate, maternal corticosteroids use, and small for gestational age (SGA). Clinical site will be used as a stratifying factor to control for any confounding by site through residual, site-level treatment imbalance. The logistic regression will be estimated using a generalized estimating equation (GEE) in order to adjust for the inherent correlation expected with multiples. Standard regression diagnostics will be used to assess model adequacy, and to examine for potential outlying or influential data points.

Prior studies offer no basis for assuming a priori interactions between treatment arms and subgroups defined by sex, race/ethnicity, gestational age, site or a combination of these groups, beyond that already controlled for in the randomization. For that reason, preplanned tests for interactions with treatment assignment are not warranted, and not powered for. We propose, however, to table all results by subgroups for descriptive purposes and to explore in secondary analyses possible subgroup differences by treatment group, solely for purposes of generating hypotheses for future studies. In particular, there is interest in exploring subgroups defined by:

- Consenting procedure which may vary by site (antenatal vs. deferred consent). While consenting procedure differences may result in some selection bias, this will be implicitly adjusted for with

the already planned clinical site stratification factor. Additionally, the sample size still results in 80% power at $\alpha=0.038$ for the primary outcome even if the selection bias results in a reduced control arm rate.

- Route of treatment (facemask vs. nasopharyngeal tube). While not expected to modify the intervention effectiveness, exploring this difference will be important for future study design and clinical practice.

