4. INTERIM ANALYSIS

Since neonatal safety is a consideration in this study, we have chosen to use a group sequential design. Thus, in addition to the final analysis, there will be two interim statistical analyses during the course of this study. The purpose of the interim analyses will be to determine whether or not there is sufficient evidence of a difference between the treatment arms in the primary endpoint such that the trial should be discontinued prior to reaching the target accrual goal.

Interim analyses will be performed after approximately 1/3 (200 subjects) and 2/3 (400 subjects) of the total required patients have completed their primary outcome. An additional safety review will be undertaken after 1/6 (100 subjects) have completed their primary outcome. The results of the interim analyses will be presented to the SAIL Data Safety and Monitoring Committee (DSMC). The primary outcome for the interim analyses will be the comparison of death/BPD between the treatment arms. This comparison will be accomplished by means of a simple generalized estimating equation (GEE) model for death/BPD versus treatment (since adjustment for deliveries with multiple babies will be needed). An approximate O'Brien-Fleming boundary will be used at each interim look to calculate the nominal significance level to which interim p-values are compared (O'Brien PC, 1979). Using the O'Brien Fleming spending function, the three analyses (2 interim + final) should use the following incremental α values (0.0002, 0.012, and 0.038) in order to achieve an overall α =0.05.

There are four comparisons to warrant early stopping: (1) Clear superiority: Superiority of the intervention is sufficiently large that the study should be discontinued because equipoise is lost and randomization should no longer proceed. (2) Futility: The evidence in favor of the intervention is such that at the completion of the study, there is inadequate power to detect an improvement and the study should be dropped. (3) Inferiority: The evidence shows that the intervention is worse than the control and the study needs to be stopped. (4) Safety: Secondary safety outcomes that are considered serious adverse events possible related to the study are clinically higher in the intervention group. (See also section 4.4 for additional safety outcomes).

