5.4 Analysis of Efficacy Endpoints

5.4.1 Primary Endpoint

In addition to the two-sample comparison (Appendix B, Table 5), adjusted analyses of the primary endpoint (death/BPD rate) may be performed. These adjusted analyses of the primary endpoint will rely on logistic regression and generalized estimating equation (GEE, to control for clustering within multiple births) methods to evaluate whether observed differences, if any, are attributable to imbalances in prognostic factors such as gender, gestational age, initial heart rate, maternal corticosteriods use, and small for gestational age (SGA). Standard regression diagnostics will be used to assess model adequacy and examine potential outlying or influential data points for these analyses. If there are clinical or demographic characteristic imbalances between the two treatment arms, a propensity score analysis (via stratification into 5 subgroups, and via inverse propensity treatment weights) will be used to assess the sensitivity of the results to any treatment allocation biases.

Prior studies offer no basis for assuming a priori interactions between treatment arms and subgroups defined by sex, race/ethnicity, gestational age, site or a combination of these groups, beyond that already controlled for in the randomization. For that reason, preplanned tests for interactions with treatment assignment are not warranted, and not powered for. We propose, however, to table all results by subgroups for descriptive purposes and to explore in secondary analyses possible subgroup differences by treatment group, solely for purposes of generating hypotheses for future studies. In particular, there is interest in exploring subgroups defined by:

- Consenting procedure which may vary by site (antenatal vs. deferred consent). While consenting procedure differences may result in some selection bias, this will be implicity adjusted for with the already planned clinical site stratification factor. Additionally, the sample size still results in 80% power at α=0.038 for the primary outcome even if the selection bias results in a reduced control arm rate.
- Route of treatment (facemask vs. nasopharyngeal tube). While not expected to modify the intervention effectiveness, exploring this difference will be important for future study design and clinical practice.

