6.2 Other Missing Data Considerations

In addition to data that is naturally missing from participants who withdraw from study, it is expected that there may be occasional missing values for other subjects. All attempts will be made to keep missing data to a minimum. Extensive procedures to minimize missing data during the data collection and entry process will be put in place, following standard operating procedures at the DCC. These procedures will be described further in the Manual of Procedures. In addition, since the infants are still hospitalized at 36 weeks PMA as part of routine clinical care, it has been our experience that this type of missing data is minimal. The number of subjects included with each individual analysis will be given with the results. In general, missing data will not be directly imputed in any way.

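### Protocol 5.1.1 adjusts the primary outcome for SNAPPE, a score taken after randomisation and treatment; that adjusted estimate does not target the total effect of SI

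*Protocol*

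**What the plan says.** Protocol 5.1.1 treats severity of initial illness as a potential confounder and states: "Adjustment for SNAPPE scores on admission to the NICU will be performed during the analysis of the primary outcome".

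The data table in Protocol section 5 describes SNAPPE as a "severity score that is compiled by using clinical parameters within the first 12 hours of life". The listed inputs include lowest pH, PaO2 with the corresponding FiO2 and mean airway pressure, urine output and seizures. For the delivery room form, the same table says "Research intervention takes place within the first 30 seconds up to 1 - 2 minutes of life". Protocol 4.6 has the envelope opened only after the infant is delivered and judged to need respiratory help.

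The analysis sections say something else. Protocol 6.1.2.2: "Potential covariates include gender, gestational age, initial heart rate, maternal corticosteroids use, and small for gestational age (SGA"). SAP 5.4.1 names the same five variables, starts from a two-sample comparison, and adds that "adjusted analyses of the primary endpoint (death/BPD rate) may be performed". The interim test in SAP section 4 (and Protocol 6.2) is a "simple generalized estimating equation (GEE) model for death/BPD versus treatment". The SAP does not mention SNAPPE anywhere.

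On missing values, SAP 6.2 says "In general, missing data will not be directly imputed in any way". SAP 6.3 promises an as-randomised comparison that includes all randomised participants.

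**The concern.** A covariate that may be affected by treatment is not a baseline confounder, and randomisation does not need help from it. The trial's first hypothesis (Protocol 2.1) is that SI reduces mechanical ventilation and surfactant use in the first week. FiO2 endpoints from the first 48 hours are secondary outcomes, and Protocol 1.1 also lists a "respiratory severity score (FIO₂ x mean airway pressure") as one. Part of SNAPPE therefore lies on the path by which SI is supposed to reduce death or BPD. Conditioning on it removes that part of the effect. If SI improves early physiology, the adjusted benefit is understated. If SI worsens it, harm is understated, which matters because SAP 2.3 makes death or BPD a safety endpoint as well.

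There are two further consequences. An infant who dies before any score exists would probably leave a SNAPPE-adjusted model, although that infant is a primary-outcome event. And because one section says the adjustment will be done while the analysis sections leave it unnamed and optional, which result counts could be settled after the data are seen.

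**Working it through.** **Order of events**

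| Event | Time | Source |
|---|---|---|
| Envelope opened | In the delivery room, once the infant is found eligible (up to 30 seconds) | Protocol 4.4.1, 4.6 |
| SI given | Within the first 1 to 2 minutes of life | Protocol 5, data table |
| SNAPPE | On NICU admission, or over the first 12 hours | Protocol 5.1.1; Protocol 5, data table |

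The two descriptions of the score's timing differ, but on either one it follows randomisation and SI.

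**The plan's own figure.** Inputs from Protocol 6.1.1: 65% vs 52.5%, two-sided alpha 0.038, power 80%. With mean rate 0.5875,

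n = [2.075·√(2·0.5875·0.4125) + 0.842·√(0.65·0.35 + 0.525·0.475)]² / 0.125² = 262.6, so 263 per arm.

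This matches the protocol. The unadjusted odds ratio is (0.525/0.475)/(0.65/0.35) = 0.60.

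**Model for the adjustment.** The documents give neither the prognostic strength of SNAPPE nor the amount by which SI might shift it, so both are assumed. Let pre-treatment severity be U ~ N(0,1), the score S = U − d·T (T = 1 for SI, d = improvement in SD), and logit P(event) = a + b·S + c·T. The values of a and c are solved by numerical integration so that the marginal rates stay at 65% and 52.5%. Then:

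- SNAPPE-adjusted OR = exp(c)
- like-for-like OR, adjusted for pre-treatment severity only = exp(c − b·d)
- hence SNAPPE-adjusted OR = like-for-like OR × exp(b·d)

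Example, b = 1, d = 0.2: a = 0.746, c = −0.425, SNAPPE-adjusted OR 0.654, like-for-like OR exp(−0.625) = 0.535. Power is for the Wald test from the expected information, 263 per arm, alpha 0.038.

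| SI improves score by | b = 1: OR (power) | b = 0.5: OR (power) |
|---|---|---|
| 0 SD | 0.54 (0.86) | 0.58 (0.82) |
| 0.1 SD | 0.59 (0.73) | 0.61 (0.74) |
| 0.2 SD | 0.65 (0.54) | 0.64 (0.64) |
| 0.32 SD | 0.74 (0.30) | 0.68 (0.51) |
| 0.63 SD | 1.00 (0.04) | 0.79 (0.20) |

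The first row is the like-for-like reference. The gap between it and 0.60 is non-collapsibility of the odds ratio, not bias. The last row is an extreme: at b = 1 it is the shift at which the whole effect runs through the score.

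A separate large simulation put the result on the risk-difference scale. With 0.8 log-odds per SD, the standardised difference is −12.6 points with no shift, −10.9 at 0.1 SD, −9.4 at 0.2 SD and −4.0 at 0.5 SD.

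**Harm case** (65% vs 75%, b = 1). The like-for-like OR is 1.77. If SI worsens the score by 0.2 SD, the adjusted OR is 1.77·exp(−0.2) = 1.45; at 0.32 SD it is 1.28.

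**Early deaths without a score.** If a fraction e of an arm dies unscored, the event rate among the rest is (p − e)/(1 − e). The loss rates are assumed.

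| True rates, control vs SI | Lost, control / SI | Rates left | Apparent benefit of SI |
|---|---|---|---|
| 65% vs 65% | 2% / 5% | 64.3% vs 63.2% | 1.1 points |
| 65% vs 65% | 5% / 2% | 63.2% vs 64.3% | −1.1 points |
| 65% vs 52.5% | 2% / 5% | 64.3% vs 50.0% | 14.3 points |
| 65% vs 52.5% | 5% / 2% | 63.2% vs 51.5% | 11.6 points |
| 65% vs 52.5% | 2% / 2% | 64.3% vs 51.5% | 12.8 points |

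**The case against.** The best defence is that Protocol 5.1.1 is not the analysis section. It says adjustment will take place during the primary-outcome analysis, not that SNAPPE enters the model on which the decision rests. The SAP leads with the two-sample comparison, makes adjusted analyses optional, and uses a treatment-only interim model. This stands, and it limits the damage to an adjusted analysis. It does not remove the problem: the method in Protocol 6.1.2.2 is itself a logistic regression allowing covariates, both covariate lists are open-ended, and nothing cancels the instruction in 5.1.1.

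Second, if SI does not change the score, adjusting for it does no harm. That is correct, as the 0 SD row shows. But the trial's rationale is that SI does change early physiology, and a model conditioning on the score does not target the total effect even where the two happen to agree.

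Third, the sizes rest on an idealised score and assumed inputs. That also stands; they are a range, not a forecast. Beyond full mediation the estimate would even cross the null (b = 1, d = 1.1: 0.535·exp(1.1) = 1.61), so a pull toward no effect describes moderate shifts only.

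Fourth, no passage says that early deaths would lack a score, or how partial scores are handled. The missing-score point is firm only for deaths before any score exists, and equal losses of 2% move the result by just 0.3 points.

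Finally, the freedom to choose between adjusted and unadjusted results comes partly from the loose covariate wording and would outlast deletion of the SNAPPE sentence. This is fair, and is a reason to tighten that wording too.

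**Conclusion.** The point holds. The timing and the mismatch between sections follow from the documents themselves and carry high confidence. An analysis done as Protocol 5.1.1 directs would give an adjusted estimate that differs from the total effect of SI whenever SI shifts the score.

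The size is conditional. For an assumed improvement of 0.1 to 0.32 SD and a score effect of 0.5 to 1 log-odds per SD, power of the adjusted test falls from 0.82–0.86 to between 0.74 and 0.30. A harmful effect would be understated in the same way. The early-death effect is smaller: about 1 to 2 points in either direction at the assumed unequal losses.

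The two-sample comparison, the interim tests and the sample size of 263 (300 after inflation) are not affected. This should be fixed, but it does not undermine the design.

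**What to change.** - Protocol 5.1.1: delete the SNAPPE adjustment of the primary outcome, or relabel it an exploratory mediation analysis that does not support the primary conclusion.
- Protocol 6.1.2.2 and SAP 5.4.1: state that only variables fixed before the envelope is opened may enter the primary model: site, gestational age, sex, antenatal steroids, SGA, and initial heart rate defined as the value at the eligibility check.
- Report SNAPPE by arm as an early outcome, with the number of infants who have no score.

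The cost is a small protocol amendment, which under Protocol section 9 needs IRB approval at the participating centres (21 sites in the protocol summary), plus one SAP sentence. No new data or patients are needed. If an amendment is unwelcome now, a SAP sentence saying that SNAPPE does not enter the primary model settles the analysis, and 5.1.1 can be corrected at the next amendment.
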